13.4 Statistical Analysis Plan

Two-tailed t tests will be used to compare clinical characteristics between patients with the Bone Allograft (control therapy) and those with the Bone Allograft/Amnion Allograft (test therapy) for continuous variables with a normal distribution. Nonparametric (Wilcoxon) tests will be used otherwise.

For categorical variables, inter-group comparisons will be conducted using chi-square tests or Fisher's Exact Test, as deemed necessary. To determine whether the groups experienced equivalent changes in bone growth from baseline to follow-up, paired t (or Wilcoxon signed-rank) and McNemar's tests will be used for continuous and categorical variables, respectively.

The α level will be set at 0.05. Statistical analysis will be carried out using SAS software version 9.2 (SAS Institute, Inc, Cary, North Carolina).

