3.0 STUDY POPULATION

3.1 Entrance Criteria

Twenty healthy adult patients (10 in each group) of any ethnicity or gender whose treatment plan includes extraction of maxillary anterior teeth and/or mandibular and/or maxillary pre-molars and their replacement with root-form dental implants will be consecutively recruited for enrollment in the study.

Participants must be at least 19 years old with demonstrated ability to understand the proposed treatment recommendations and prognosis and be able to provide informed consent, in English, without the aid of ad-hoc translation from another language. Decisionally-impaired adults and/or minors, who cannot consent for themselves, will not be enrolled; women who are pregnant or lactating at the time of enrollment will not be included. Women will be tested for current pregnancy status.

Prior to enrollment, prospective participants must agree to be available for the entire duration of the study, be compliant with needed study-related evaluations and demonstrate a willingness to comply with strict time-line requirements. Certain health and medication exclusions apply (table 1).

Table 1 Entrance Criteria

Inclusion	Exclusion
Existence of one or more non-adjacent teeth in the aesthetic zone that are scheduled for extraction	Pregnancy or lactating at the time of enrollment
Healthy enough to undergo the proposed therapy without compromise to their existing health status	Previous malignant neoplasm
Demonstrated willingness to comply fully with protocol time-line and procedural requirements	A known hypersensitivity to DBM
At least nineteen years old	A known hypersensitivity to Titanium metal
Able to read and understand written English without the aid of ad hoc interpretation	Any health condition that in the opinion of the clinical investigators may adversely affect bone healing
Able to cognitively understand the proposed study therapy and possible prognosis	Any medication that in the opinion of the clinical investigators may adversely affect bone healing
Able to consent for their own inclusion in the study	Any indication of an inability to make autonomous decisions

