4.5 Surgical Extractions

All surgeries will be performed by qualified clinicians/investigators in an appropriately equipped surgical operatory located in the Periodontal Clinic at UAB School of Dentistry.

Prior to extraction surgery, participants will be given a loading dose of antibiotics based on their medical history and concomitant medications. A suggested prophylactic regimen follows:

2 gm of Amoxicillin 1 hour prior to the procedure followed by 500 mg (TID) for 7 days
Patients with reported allergy to Amoxicillin:
600mg Clindamycin 1 hour prior to the procedure followed by 300 mg (TID) for 7 days

The facial area will be scrubbed with 2% Clorhexidine soap and the oral cavity disinfected by rinsing for 1 minute with a 0.12% chlorhexidine gluconate antimicrobial oral rinse. Prior to extractions clinical photographs will be taken from the buccal and occlusal aspects. Photographs will be taken in a 1:1 ratio using a Nikon D-7000.

After preparation and isolation of the surgical area, anesthesia will be achieved in the region by regional block or local infiltration. Conscious sedation may be added at the surgeon's discretion to help manage patient anxiety.

The teeth will be extracted as atraumatically as possible, without raising a flap, utilizing periotomes, luxators and the Easy Extrac system. In both groups, the integrity of the remaining socket walls will be assessed and measurements recorded on the surgical CRF. The sockets will be debrided and a bleeding surface created by decorticate the socket walls with either a curette or a surgical round burr.

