4.6 Grafting Extraction Sockets

After extractions, sockets will be grafted according to each participant's assigned randomization group.

Group-1: Each socket will be grafted with Bone Allograft mixed with sterile saline.

4.6.1a Irrigate sockets with sterile saline.

4.6.1b Pack the graft into each of the study sites using mild pressure achieving complete fill of the sockets.

4.6.1c Trim a 3 mm section of collagen plug and secure it over the grafted areas with 5.0 Monocryl crossing mattress sutures.

Group-2: Each socket will be grafted with Amnion Graft mixed with Bone Allograft

4.6.2a Irrigate sockets with sterile saline.

4.6.2b Pack the graft into each of the study sites using mild pressure achieving complete fill of the sockets.

4.6.2c Trim a 3 mm section of collagen plug and secure it over the grafted areas with 5.0 or 6.0 Monocryl crossing mattress sutures.

After completion of procedures, the Essix retainer will be fitted and placed.

A baseline, post-grafting CBCT scan will be made to include images of each study site. Prescriptions for anti-bacterial mouth wash, antibiotics, and pain relief will be provided based on individual patient

needs. An ice-pack will be dispensed. Verbal and written home care instructions will be given and the patient will be scheduled for a follow-up appointment.

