4.7 Surgical Extraction Data Collection

The following data points will be collected and recorded on the surgical CRF: A description of the integrity of each of the socket walls will be recorded as follows.

4.7.1 Measurements of the Mesio-distal distance and the buco-lingual distance of the socket walls.

4.7.2 Measurements of dehiscence and fenestration defects made with a UNC-15 periodontal probe in relation to the adjacent socket crest and rounded up to the nearest millimeter.

4.7.3 Wound Measurements – Mesio-distal distance and bucco-lingual distance of the soft tissue wound margins after suturing made with a UNC-15 periodontal probe and rounded to the nearest millimeter.

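### The between-arm tests in section 13.4 are valid, but they leave out baseline ridge and socket measurements already collected and so give up precision with 10 participants per arm

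*Combined protocol and SAP*

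**What the plan says.** The between-arm analysis of continuous outcomes is set out in section 13.4 and repeated in the synopsis: "Two-tailed t tests will be used to compare clinical characteristics between patients with the Bone Allograft (control therapy", set against patients in the test arm. For variables that are not normal, "Nonparametric (Wilcoxon) tests will be used otherwise". Neither place names a covariate or a regression model. For change in bone growth from baseline to follow-up, 13.4 says that "paired t (or Wilcoxon signed-rank) and McNemar's tests will be used for continuous and categorical variables, respectively".

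The same protocol collects starting values. Section 4.5 states: "In both groups, the integrity of the remaining socket walls will be assessed and measurements recorded on the surgical CRF". Section 4.7 lists the mesio-distal and bucco-lingual socket distances (4.7.1) and, in 4.7.2, "Measurements of dehiscence and fenestration defects made with a UNC-15 periodontal probe in relation to the adjacent socket crest". Section 4.6 adds: "A baseline, post-grafting CBCT scan will be made to include images of each study site".

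The trial enrols "Twenty healthy adult patients (10 in each group) of any ethnicity or gender". Randomization is stratified by smoking status only (4.2). Table 1 has no criterion on socket walls, and section 3.1 admits maxillary anterior teeth and premolars of either jaw. Aims 2 and 4 (section 2.3) and the histomorphometry in 13.1 are between-group comparisons.

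**The concern.** Sockets can differ at the start in size and in wall loss, and neither entry nor allocation limits this. If starting dimensions predict week-7 dimensions, an unadjusted comparison carries that variation as noise. In a trial this small, the arms may also differ at the start by an amount that matters, and the named tests have no means of allowing for it.

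What is at stake is the sensitivity of the Hypothesis-2 comparisons, and how far the observed difference can be trusted if the arms turn out unequal at V-2. If no covariate is fixed in advance, any adjustment made after an imbalance is seen will be open to the charge of being chosen post hoc.

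**Working it through.** **Inputs from the documents.** There are 10 participants per arm (3.1). The tests are two-tailed, and "The α level will be set at 0.05" (13.4). The documents give no power, effect size, SD or correlation, so there is no stated calculation to reproduce.

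**Assumptions.** The true difference is 1.0 SD of the outcome. The correlation ρ between covariate and outcome runs from 0 to 0.7. Variables are normal, with one value per participant.

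**1. Chance imbalance.** The difference between arm means of a standardized baseline measure has SD √(2/10) = 0.447. So P(|difference| > 0.5 SD) = 2[1 − Φ(0.5/0.447)] = 26%, and P(|difference| > 0.8 SD) = 7%.

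For a yes/no feature such as a wall defect, take two independent Binomial(10, p) counts. The probability that the arms differ by 3 or more participants is 6%, 16%, 22% or 26% for p = 10%, 20%, 30% or 50%. These values of p are also assumptions.

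**2. Power of the planned t test.** The noncentrality is 1.0/0.447 = 2.236 on 18 df, which gives 56%. The difference detectable with 80% power is 1.32 SD.

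**3. Power of ANCOVA with one covariate.** The standard error is √[(1 − ρ²) × (2/10) × (1 + 1/16)] on 17 df, where 1 + 1/16 is the expected cost of estimating the slope, 1 + 1/(2n − 4) with n = 10. For ρ = 0.5 this is √(0.75 × 0.2 × 1.0625) = 0.399, so the noncentrality is 2.505. The formula is approximate; the simulated column comes from repeated trials of 10 against 10.

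| ρ | Power, formula | Power, simulated | Detectable difference at 80% power (formula) |
|---|---|---|---|
| 0 | 53% | 54% | 1.37 SD |
| 0.1 | – | 54% | – |
| 0.3 | 57% | 58% | 1.31 SD |
| 0.5 | 66% | 66% | 1.19 SD |
| 0.6 | 72% | 73% | 1.10 SD |
| 0.7 | 82% | 82% | 0.98 SD |

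The unadjusted t test stays at 56% throughout.

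**4. Type I error.** Over all randomizations both methods hold 5% in simulation. Among trials with a baseline imbalance above 0.5 SD, the unadjusted test rejects a true null in about 9% (ρ = 0.5) or 13% (ρ = 0.7). Above 0.8 SD the figures are about 15% and 25%. ANCOVA stays at about 5% in each case. The reason is that an imbalance of 0.5 SD shifts the unadjusted difference by ρ × 0.5, which is 0.25 SD at ρ = 0.5.

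**5. The change-from-baseline sentence.** Paired t, signed-rank and McNemar tests ask whether values moved within patients. Run in each arm, they adjust no comparison between arms. A between-arm test on change scores is not named. If it were used (equal variances assumed), power would be 56%, 66% and 78% at ρ = 0.5, 0.6 and 0.7, against 66%, 73% and 82% for ANCOVA.

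**The case against.** The strongest reply is that randomization already makes the planned tests valid. That stands. A reader might infer that a chance excess of damaged sockets biases the trial and would pass for a graft effect. The documents do not support this: chance imbalance is already counted in the 5% error, and what remains is lost precision and conditional error in unlucky allocations.

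A reader might also infer that no analysis uses the baseline data. This goes too far. The change sentence in 13.4 and the synopsis outcome on osseous change over time both imply some use of the V-2 CBCT. If the arms were compared on change, part of the ridge-size problem would shrink (working, step 5). But that test is not specified, and a ridge change score would not account for wall defects.

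The gain rests on correlations that the documents do not give. This stands too. It is best supported for a ridge dimension adjusted for its own earlier value, and weakest for histology or torque adjusted for a socket defect.

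Four cautions limit the covariate choice:

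- Dehiscence averaged over up to four sites does not match a biopsy from one site, and many dehiscence values may be zero.
- The V-2 scan follows grafting, so bone fill measured on it already includes graft.
- Table 2 places randomization at V-1, before the socket is measured, and only laboratory technicians are stated to be blinded (6.3). A surgeon's measurement could be influenced by known allocation.
- Wound margins (4.7.3) are taken after suturing and are not pre-graft values.

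Finally, the only parameter that 13.3 labels primary is implant survival, which this point does not touch.

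**Conclusion.** The point holds as a matter of efficiency and of robustness to chance imbalance; it does not show an invalid test. Section 13.4 specifies no baseline-adjusted comparison between arms, although the data for one are collected. At 10 per arm and a 1.0 SD difference, adjustment changes power from 56% to between 58% and 82% for ρ of 0.3 to 0.7, and to about 54% for ρ of 0 to 0.1. A baseline imbalance above 0.5 SD has probability 26%.

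The omission is certain from the text; the size of the gain is conditional on ρ. Use of the V-2 ridge dimension as a baseline further assumes that the outer ridge measured just after grafting does not depend on which graft was packed. The documents do not support a blanket replacement of every unadjusted test.

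**What to change.** In 13.4 and the synopsis:

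1. **Week-7 ridge dimensions.** Make the between-arm test an ANCOVA (rank ANCOVA if skewed) on one value per participant, adjusted for the same dimension on the V-2 CBCT. Where a participant has several sites, state how they are combined, and combine baseline and outcome in the same way.
2. **Outcomes with no baseline of their own** (% new bone, torque, and CBCT bone fill because the V-2 scan already contains graft). An adjusted analysis may be added using one pre-specified pre-graft socket measure from 4.7.1 or 4.7.2. Take it from the same site or sites as the outcome, which for histology means the biopsied site. Report the unadjusted test as well.
3. **Safeguards.** Name each covariate before data are seen, and limit it to one per outcome. Require the socket measurements to be entered on the surgical CRF before the graft type is known.

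The cost is wording in the SAP and synopsis, a CRF sequencing instruction, and one degree of freedom. If the correlation is near zero, 2 to 3 points of power are lost. No new measurement, visit or participant is needed.

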Objectives	
To evaluate and compare post-treatment healing of hard and soft tissues in maxillary or mandibular aesthetic zones following procedures utilizing test and control grafting materials.
 
To evaluate longitudinal clinical outcome of dental implants surgically inserted into regenerated bone 8 weeks after tooth extraction and grafting.

Null	The following null hypothesis will be tested: there is no difference in post-extraction healing patterns between extraction sockets grafted with Bone Allograft (BA) and extraction sockets grafted

Hypotheses	with Bone Allograft + Amnion Allograft.
Randomization	
Participants will be stratified for smoking status and randomized to one of two treatment groups:
 
Test Group-1: Atraumatic extractions followed by Bone Allograft (BA) and collagen plug
 
Test Group-2: Atraumatic extractions followed by Bone Allograft/Amnion Allograft (AA) and collagen plug

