	
Implants Exposed Mandibular implants will be exposed after approximately 4 months; maxillary implants will be uncovered after approximately 6 months.
 
Implant Restoration Implants will be restored in the conventional manner with aesthetically pleasing cemented single crown restorations by one of the investigators. Photographs and radiographs will be obtained at permanent restoration.
 
Longitudinal Follow-up Two annual follow-up evaluations will be completed at 12 months and 24 months from the date the permanent restoration is attached to the implant. Each assessment will include:
 
 Standardized intra-oral periapical dental radiographs Clinical photographs Measurement of clinical parameters Assessment of soft-tissue contours Assessment of overall aesthetics Assessment of implant/restoration interface
Population	
Twenty healthy adult patients (10 per group) of any ethnicity or gender whose treatment plan includes extraction of mandibular and/or maxillary pre-molars and/or maxillary anterior teeth and their replacement with root-form dental implants and who meet the entrance eligibility criteria will be consecutively recruited for enrollment in the study. See inclusion/exclusion criteria – Table 1.

Outcomes	
Histology and histomorphometric analyses (site biopsies)
 
Soft-Tissue aesthetic assessments (Jemp Indices and photographs)
 
Soft Tissue Health (PI & GI, and photographs)
 
Bone Support to Implants (standardized PA radiographs and image analysis)
 
Radiographic image analysis of osseous architecture changes at study sites over time

Statistical Analyses Plan	
Two-tailed t tests will be used to compare clinical characteristics between the test and control therapies for continuous variables with a normal distribution. Nonparametric (Wilcoxon) tests will be used otherwise.
 
For categorical variables, inter-group comparisons will be conducted using chi-square tests or Fisher's Exact Test, as deemed necessary.
 
To determine whether the groups experienced equivalent changes in bone growth from baseline to follow-up, paired t (or Wilcoxon signed-rank) and McNemar's tests will be used for continuous and categorical variables, respectively. The α level will be set at 0.05.
 
Statistical analysis will be carried out using SAS software version 9.2 (SAS Institute, Inc, Cary, North Carolina).

[figure not shown]

Table of Contents

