2.3 Hypotheses and Specific Aims

The trial will test two hypotheses:

Hypothesis-1: Grafting with Bone Allograft is an efficacious method of enhancing the development of new bone fill in extraction sockets.

Hypothesis-2: Bone Allograft/Amniotic allograft will aid osseous healing and will preserve alveolar ridge dimensions of extraction sockets more effectively than extraction sites grafted with Bone Allograft alone.

Specific Aims

- 1: Compare the efficacy of bone grafting with and without enrichment with amnion.
- 2: Compare alveolar ridge dimensions between groups after 7 weeks of post-extraction healing.
- 3: Compare soft tissue healing between groups at week-1, week-2, week-4 and after 7 weeks of post-extraction healing.

- 4: Assess quantitative bone fill between groups after 7 weeks of post-extraction healing
- 5: Compare qualitative bone fill between groups after 7 weeks of post-extraction healing.
- 6: Assess and compare the relationship of osseous healing and implant stability at insertion across groups after 8 weeks of post-extraction healing.
- 7: Compare implant stability between groups at 12 months and 24 months post-restoration.
- 8: Assess changes in longitudinal crestal bone level between groups at 12 and 24 months after permanent prosthetic attachment.

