4.2 Randomization

Participants will be stratified for smoking status and randomized to one of two extraction/grafting groups. In the case of multiple tooth sites within one participant, all the tooth sites will be assigned to receive the same graft material.

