13.3 Outcome Endpoints

The primary efficacy parameter for implant success will be the duration of implant survival from surgical placement to 24 months post-placement across all groups. Measurement of bone height along the implant mesial and distal surfaces at 12 and 24-month follow-up evaluations will be captured from radiographic images and compared to same measurements at insertion. These measurements will be used to derive changes from baseline values.

Efficacy endpoints will include implant and prosthesis function as assessed by gingival health, bone levels and participant subjective satisfaction with the study therapy. Differences between groups will

be calculated and used to determine if osseous changes and implant function are different between groups.

Safety will be evaluated by clinical signs and symptoms of dental and medical events.

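### Section 13.4 assigns paired tests to the between-group question on bone change; in this parallel-group trial they can show neither a graft difference nor equivalence

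*Combined protocol and SAP*

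**What the plan says.** Section 13.4 opens with between-group tests: "Two-tailed t tests will be used to compare clinical characteristics between patients with the Bone Allograft (control therapy" and those on the test therapy, with Wilcoxon tests for non-normal data. It then gives chi-square or Fisher's exact tests for categorical comparisons between groups. The next sentence turns to bone: "To determine whether the groups experienced equivalent changes in bone growth from baseline to follow-up, paired t (or Wilcoxon signed-rank" tests are to be used for continuous variables and McNemar's test for categorical ones. The synopsis (Statistical Analyses Plan) repeats this.

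The questions the trial asks are between-group:

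- The synopsis null hypothesis is that "there is no difference in post-extraction healing patterns between extraction sockets grafted with Bone Allograft (BA" and those that also receive amnion.
- Hypothesis-2 (section 2.3) says that the amnion combination "will preserve alveolar ridge dimensions of extraction sockets more effectively than extraction sites grafted with Bone Allograft alone".
- Aim 8 (section 2.3) is to "Assess changes in longitudinal crestal bone level between groups at 12 and 24 months after permanent prosthetic attachment".
- Section 13.3 says that differences between groups will "be calculated and used to determine if osseous changes and implant function are different between groups". It names no test.

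On design, section 4.2 randomizes each participant to one of two groups and adds: "In the case of multiple tooth sites within one participant, all the tooth sites will be assigned to receive the same graft material".

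**The concern.** A paired test needs two measurements on the same unit. Here the only such pair is baseline and follow-up, so the test asks whether bone changed over time. The sentence in section 13.4 asks something else: whether the two groups changed alike. An analyst who follows it literally produces a p-value for change in each arm, or one pooled over both arms, and neither bears on the null hypothesis or on Hypothesis-2. An analyst who switches to a two-sample test of change makes a sound choice, but one the plan has not clearly fixed in advance.

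The word 'equivalent' adds a second problem. No margin appears anywhere, the stated null is no difference, and Hypothesis-2 is a superiority claim. Neither a paired test nor a non-significant difference test can establish equivalence.

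**Working it through.** **Inputs from the documents.** 10 participants per group (section 3.1); two-sided alpha 0.05 (section 13.4); one graft per participant (section 4.2); one or more sites (Table 1), at most four (section 4.1). CBCT is taken after grafting and at week 7 (section 5.0); radiographic bone height is compared with insertion (section 13.3). Section 13.4 ties 'bone growth' to no measure, so I take it to mean these two, which have a baseline. The documents give no effect size, SD or power figure, so there is no planned figure to reproduce. Effects below are assumptions in units of the SD of participant-level change.

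**Step 1: what each test estimates.** The within-arm paired t test has 9 df, critical value 2.262 and noncentrality d√10, where d is the true change in that arm. Pooled over both arms it has noncentrality d√20 when the grafts do not differ. Neither expression contains the graft contrast. The two-sample test of change has 18 df, critical value 2.101 and noncentrality δ√(10/2), where δ is the difference between arms.

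**Step 2: what happens if the two within-arm p-values are compared.** Let p be the power of one arm's paired test. With identical grafts, exactly one arm is significant with probability 2p(1−p). With different grafts it is p₁(1−p₂) + p₂(1−p₁). At d = 0.7, p = 0.506, giving 2 × 0.506 × 0.494 = 0.50. For 0.7 against 1.7, p₂ = 0.997, giving 0.506 × 0.003 + 0.997 × 0.494 = 0.49.

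| Control change (SD) | p | Arms disagree, identical grafts | Arms disagree, grafts 1.0 SD apart |
|---|---|---|---|
| 0 | 5.0% | 9.5% | 77% |
| 0.3 | 13.6% | 24% | 83% |
| 0.5 | 29.3% | 41% | 70% |
| 0.7 | 50.6% | 50% | 49% |
| 1.0 | 80.3% | 32% | 20% |
| 1.2 | 92.0% | 15% | 8% |
| 1.5 | 98.7% | 2.5% | 1.3% |

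Below 0.7 SD, disagreement is more frequent when the grafts differ. At 0.7 SD it is equally frequent, and from 1.0 SD upwards it is less frequent. At 1.5 against 2.5 SD both arms are significant in 98.7% of trials despite the difference.

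**Step 3: the pooled version.** With no graft difference, a paired test on all 20 is significant in 25%, 56%, 84% and 99% of trials at changes of 0.3, 0.5, 0.7 and 1.0 SD. It detects change, not a graft effect.

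**Step 4: the two-sample test.** Type I error is 5% whatever the common change. Power is 56% at δ = 1.0, 80% at about 1.32 and 89% at 1.5. The 95% CI half-width is 2.101 × √(2/10) = 0.94 SD.

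**Step 5: several sites per participant.** Simulated type I error of a two-sample test that treats sites as independent, at assumed intra-participant correlations of 0.2 / 0.5 / 0.7:

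| Sites per participant | Type I error |
|---|---|
| 1 | about 5% throughout |
| 2 | 7 / 11 / 14% |
| 3 | 10 / 17 / 22% |
| 4 | 12 / 22 / 28% |
| Assumed mix: 70/20/5/5% with 1/2/3/4 sites | 7 / 10 / 12% |

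A test on participant means stays at about 5% in every case.

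**The case against.** The strongest reply is that the plan already contains the right method. Section 13.3 derives changes from baseline and then calls for differences between groups; the first sentence of 13.4 compares patients on the two therapies and could be applied to a change score. The categorical sentence in 13.4 gives chi-square or Fisher's tests for inter-group comparisons without limiting them to clinical characteristics. Aims 2, 4 and 5 can be read as single comparisons at week 7 that need no change score. This stands to the extent that a reader should not infer that the plan has no between-group method. It does not rescue the sentence: 13.3 names no test, the continuous two-sample tests are listed for clinical characteristics, and the one sentence about bone change names paired tests.

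A second reply concerns Hypothesis-1, that Bone Allograft itself enhances new bone fill. With no ungrafted arm (section 4.3), within-arm change is the only baseline-to-follow-up evidence available for it, weak as that is. This stands, so the paired tests should be kept for that purpose.

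A third reply is that the disagreement rates score a rule the plan never states. That is also correct. A reader might take 50% as this trial's false-positive rate, but the documents do not support that. The rates illustrate what follows if the within-arm p-values are set against each other, at assumed effect sizes.

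**Conclusion.** The sentence is wrong as written, in both places, and should be corrected before analysis. The mismatch between test and question follows from the design alone and needs no assumption; reading 'equivalent' loosely as 'the same' does not remove it. The figures in steps 2 to 4 rest on normal data and assumed changes in SD units.

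The reach is limited. A reader might infer that the whole efficacy analysis fails. It does not: biopsy percentages and insertion torque are measured once, and implant survival, which section 13.3 makes primary for implant success, is not a change from baseline. Nor do the documents show that site clustering will inflate error by 7–28%. That range requires every participant to have 2–4 sites; one site each gives no inflation, and the assumed mostly-one-site mix gives about 7–12%.

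**What to change.** In section 13.4 and the synopsis, replace the paired-test sentence with:

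> For each bone measure with a baseline, change from baseline will be averaged over a participant's study sites with both measurements and compared between groups with a two-sample t test (Wilcoxon rank-sum if non-normal), reporting the difference with its 95% CI. Categorical bone outcomes will be compared between groups with the chi-square or Fisher's exact test already named, one result per participant. Paired and McNemar tests will be used only for change within a group, including the within-arm description relevant to Hypothesis-1, and not to compare groups.

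Delete 'equivalent', and refer to this test in section 13.3.

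Two details need a decision. If one site supplies the categorical result, choose it by a rule fixed before allocation is known; Table 2 puts biopsy site selection and randomization at the same visit, so the biopsy site is not shown to be chosen before allocation. The plan must also say whether sites exited under section 11.1 that have both scans are counted. A site judged unsuitable after review of the scans (section 4.9) can have both, and leaving it out would remove poor results.

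The change costs wording only and needs no new data. Its price is candour about precision: with a half-width of about 0.94 SD, a non-significant result must not be reported as equivalence.
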